eCRF	Electronic Case Report Form
ET	Early Termination
EDC	Electronic Data Capture system
IMP	Investigational Medicinal Product
IRB	Institutional Review Board
PI	Principal Investigator
PICC	Peripherally inserted central catheter line
RCT	Randomized Controlled Trial
RIC	Respiratory Illness Clinic
SAE	Serious Adverse Event
SARS	Severe Acute Respiratory Syndrome
SC	Subcutaneous
WOCBP	Women of Childbearing Potential
BMP	Basic Metabolic Panel
AST	Aspartate Aminotransferase
ALT	Alanine Transaminase
AP	Alkaline Phosphatase
TBili	Total Bilirubin
TCRC	Translational and Clinical Research Center
DBili	Direct Bilirubin

I. Introduction

A novel strain of coronavirus (COVID-19) was recently detected in Wuhan, China and reported to the World Health Organization Country Office in China on December 31st 2019. Although respiratory symptoms are absent or mild in the majority of patients, COVID-19 infection is associated with a 4% mortality rate due to the development of acute respiratory distress syndrome, mainly among elderly individuals and those with comorbid conditions. Despite global efforts to contain viral spread, the incidence of COVID-19 continues to rise exponentially. The United States has entered an indefinite period of lockdown, with the current crisis likely to incur an immense socioeconomic burden. At present, there are no vaccines available for disease prevention. Therefore, identifying effective treatment strategies to curb human-to-human transmission, while reducing disease severity and shortening hospital and ICU admissions, is an area of urgent and unmet clinical need.

Peginterferon lambda-1a (Lambda) is a conjugate of recombinant human interleukin 29 (rIL-29) and a linear polyethylene glycol (PEG) chain, and has been identified as a therapeutic candidate. Lambda has been extensively trialled as a treatment for chronic hepatitis B, C and D, and its safety and tolerability have been demonstrated for up to 48 weeks of treatment, with over 3000 patients dosed with an excellent safety record. Lambda targets type III IFN receptors, whose expression is primarily restricted to the lungs, intestine, and liver. This is likely to account for the fewer off-target effects associated with use of Lambda versus other trialled interferons.

Murine studies also indicate robust antiviral effects of IFN lambdas against SARS-CoV, influenza, rotavirus, norovirus and reovirus¹. Furthermore, SARS-CoV replicated to high titers and induced signs of disease in mice lacking both type I and type III IFN receptors. These effects were not observed in single-knockout mice expressing either type I or type III IFN receptors, indicating protective roles for both type I and type III IFNs against SARS-CoV². In addition, treatment of influenza A-infected mice with IFN lambda significantly increased their survival and reduced morbidity. Treatment with IFN alpha demonstrated comparable antiviral activity, however it exerted proinflammatory effects on immune cells, with an associated increase in mortality. **Hence, IFN lambda derivatives may represent a superior treatment option compared to IFN alpha.**

The potential benefit of IFN-based therapy in the management of coronavirus infection was evaluated in a preliminary study of patients admitted to hospital with probable SARS-CoV in 2003³. Administration of IFN alfacon-1, a synthetic recombinant type I IFN, plus corticosteroids was associated with more rapid resolution of radiographic lung abnormalities and improved oxygen saturation levels compared to treatment with corticosteroids alone.

On the basis of these preliminary findings, it is highly plausible that treatment with Lambda will promote COVID-19 clearance and improve clinical outcomes. However, to date, evidence in humans is lacking. We propose to evaluate the safety, efficacy and tolerability of Lambda treatment versus standard of care in hospitalized patients with confirmed COVID-19 infection. We will conduct a randomized controlled trial (RCT) of subjects diagnosed with COVID-19 infection by PCR analysis of nasopharyngeal secretions. Subjects will be randomized 1:1 to receive Lambda 180 mcg SC or saline injection. The primary endpoint is rate of PCR negativity on post-treatment Day 7.

II. Objectives

Primary Objectives

The primary objective of this study is as follows:

- To assess the efficacy of Lambda (180 mcg SC injections) vs. saline placebo injection in inducing PCR negativity at day 7 among subjects hospitalized with COVID-19 infection

Secondary Objectives

The secondary objectives of this study are as follows:

- To assess the efficacy of Lambda (180 mcg SC injections) vs. saline placebo injection in inducing PCR negativity at days 3, 7 and 14 among hospitalized subjects with symptomatic COVID-19 infection
- To assess the efficacy of Lambda (180 mcg SC injections) vs. saline placebo injection in inducing symptomatic improvement in subjects with COVID-19 infection, assessed by daily symptom questionnaire
- To assess the efficacy of Lambda (180 mcg SC injections) vs. saline placebo injection in improving clinical outcomes (death, ICU stay, intubation) in subjects hospitalized with COVID-19 infection
- To evaluate the safety and tolerability of Lambda (180 mcg SC injections) vs. saline placebo injection

III. Study Design

This is a prospective randomized trial to assess the antiviral efficacy of Lambda (180 mcg SC injection) vs. standard of care in up to 20 subjects hospitalized with COVID-19 infection.

Visit schedule

After referral by the care team and informed consent, and once the subject is confirmed as COVID-19 positive on clinical testing, patients will have initial clinical lab testing performed during baseline (visit 1). After confirmation of inclusion criteria, patients will be randomized 1:1 to receive the first dose of Lambda or saline placebo at the baseline visit (visit 1). Nasal swabs for PCR analysis will be collected for all subjects on Days 3, 7 and 14. An optional Day 5 nasal swab collection will occur only for subject who remain hospitalized on Day 5. On day 7, subjects in the treatment arm will receive a second Lambda injection and subjects in the control arm will receive a second saline placebo injection. On Day 14, subjects will undergo laboratory measurements to confirm CBC and LFT values are within safe parameters. Research blood will be collected and stored for future testing to measure levels of pro-inflammatory cytokines (e.g. IFN- γ , IL-6, IP-10, MCP-1, TNF- α). Measurements will be performed using excess blood collected for clinical purposes wherever possible. Subjects will complete a daily symptom questionnaire from screening through Day 14 ([Appendix 5](#)).

Administration of Treatment

Upto an initial 30 hospitalized patients will be enrolled (consented), with a goal of 20 subjects randomized 1:1 to receive either Lambda 180 mcg SC injections or saline placebo injections.

Administration of first dose Lambda/placebo in relation to initial COVID-19 symptom onset will be documented in all subjects.

Stopping Rules and Treatment Discontinuation

If a subject discontinues study dosing (for example, as a result of an adverse event [AE]), every attempt should be made to keep the subject in the study, and continue to perform the required study-related follow-up procedures ([Appendix 2](#)). If this is not possible or acceptable to the subject or Investigator, the subject may be withdrawn from the study

There is no option for Lambda dose reduction due to toxicity. If Lambda is withheld due to toxicity, the subject must discontinue treatment and be approached for willingness to complete remaining study visits as follow-up or to schedule an Early Termination (ET) visit as soon as possible. For subjects discharged from the hospital, the ET visit should be conducted over telephone. An in-person evaluation may be scheduled if this is deemed necessary by the overall study PI. For subjects who elect to discontinue treatment and decline the day 7 dose, study staff will confirm willingness to continue on protocol and complete all other assessments as listed in the schedule of events. For subjects unwilling to complete these assessments, an ET visit will be completed.

When medically feasible, the PI must be consulted prior to subject discontinuation.

Study drug must be discontinued in the following instances:

- Unacceptable toxicity (as defined [below](#)) or toxicity that, in the judgment of the investigator, compromises the ability to continue study-specific procedures or is considered to not be in the subject's best interest
- Pregnancy in a female subject
- Significant protocol violation that impacts subject safety
- Subject request to discontinue for any reason; it is important to determine whether the withdrawal of consent is primarily due to an AE, lack of efficacy, or other reason
- Subject noncompliance
- Discontinuation of the study at the request of the study sponsor, regulatory agency or an Institutional Review Board (IRB)

Toxicity Based Stopping Criteria

Subjects who meet any of the following laboratory or adverse event criteria must stop treatment with study drug:

- Any Grade 4 adverse event assessed as related to study drug

IV. Subject Population

Inclusion Criteria

1. Willing and able to provide informed consent
2. Male or female age \geq 18 years at time of consent
3. Hospitalized with confirmed COVID-19 infection by PCR analysis of respiratory secretions

- a. Historic diagnosis by PCR test may be at any time prior to hospitalization but subject must have documentation of a positive SARS-CoV-2 RT-PCR test within 72 hours of randomization
4. Female subjects of childbearing potential who engage in heterosexual intercourse must agree to use protocol specified method(s) of contraception as described in [Appendix 4](#)
5. Subject must be able to comply with the dosing instructions for study drug administration and able to complete the study schedule of assessments

Exclusion Criteria

1. Current or prior history of any of the following:
 - a. Clinically-significant illness or any other major medical disorder that in the opinion of the investigator, may interfere with subject treatment, assessment or compliance with the protocol
 - b. Treatment with IFN or other immunomodulatory/immunosuppressive agent within 12 months before screening.
 - c. Respiratory compromise requiring ventilatory support other than nasal cannula (mask, bipap or intubation and mechanical ventilation).
 - d. History of treatment with any of the following medications within five half-lives or 30 days before administration of the study drug (whichever is longer): anti-IL-6, anti-IL6R antagonists, Janus kinase inhibitors, ustekinumab (anti-IL-12/23), or anti IL-23 agents (guselkumab).
2. Pregnant or Nursing Females (a negative pregnancy test (urine or serum) is required during screening [if historic negative result within 48 hours prior to consent is not available] for WOCBP)
3. Life threatening SAE during the screening period
4. Subjects having the following laboratory parameters at screening
 - a. Platelet count <90,000 cells/mm³
 - b. WBC count <3,000 cells/mm³
 - c. ANC <1,500 cells/mm³
 - d. Hb <11 g/dL for women and <12 g/dL for men
 - e. CrCl < 50 mL/min
 - f. Direct Bilirubin level $\geq 1.5 \times$ ULN
 - g. INR ≥ 1.5 (except in the setting of concomitant anticoagulant use)
 - h. CRP >200 mg/L
5. Females who may wish to become pregnant and/or plan to undergo egg harvesting during the course of the study and up to 30 days of the last dose of study drug. WOCBP must abstain from breastfeeding and be willing to use effective birth control during through the week 4 post treatment follow-up visit.
6. Clinically-relevant alcohol or drug abuse within 12 months of screening. Use of any prohibited concomitant medications as described in [Section V](#)
7. Known hypersensitivity to IFN
8. Current or planned participation in an investigational new drug (IND) trial from 30-days prior to randomization through Day 14 post treatment.
9. History of full COVID-19 vaccination
 - a. Full vaccination is defined as >2 weeks post final vaccination dose

V. Investigational Product

Randomization, Blinding and Treatment Codes

This is a randomized, single-blinded controlled study. Subjects will be randomized 1:1 to receive Lambda 180 mcg SC injections vs. saline placebo injections.

Description and Handling

Lambda Formulation

Lambda injection is a sterile, nonpyrogenic, ready to use solution (0.4 mg/mL) that is clear to opalescent, colorless to pale yellow, and is essentially free of particles. Lambda injection is provided in a 1-mL long Type I glass syringe with a 29-gauge, ½-inch, thin-walled needle. The syringes are prefilled with a solution of Lambda Injection, mannitol, L-histidine, polysorbate 80, hydrochloric acid, and water for injections; they are intended for a single use (180 mcg dose). The study drug will be donated by Eiger Biopharmaceuticals. Swab kits and RT-PCR testing will be supplied by a contract research organization, Viroclinics.

Lambda Packaging and Labeling

Storage of the study drug will be done in the Massachusetts General Hospital Clinical Trials Pharmacy (MGH CTP) (directed by [name], PharmD). Study drug will be packaged and labeled per the Massachusetts General Hospital Investigational Pharmacy standard procedure and will adhere to federal guidelines.

Lambda Storage and Handling

Prefilled syringes should be stored in a refrigerator at 2 - 8°C (36 - 46°F) and protected from long-term (>24 hours) exposure to light. Lambda Injections should not be frozen. Until administered to the subjects, syringes containing the study drug should be stored in a secure area, accessible only to authorized site personnel or vendor (in the case of home health visits). During transport to subject homes (via ambulance vehicle for home health visits only), drug should be stored in a cooler with an ice pack. To ensure the stability and proper identification, study drugs should not be stored in a container other than the container in which they were supplied.

Saline Placebo

In this single blind study, saline placebo injections will be prepared by the MGH CTP. Under the direction of the lead pharmacist, pharmacy staff will prepare the placebo injections by drawing up approximately 0.45 ml of sterile saline into a 1 ml Monoject Tuberculin Safety Syringe with a 28 gauge, ½ inch, thin walled needle. Placebo injections will be labeled with standard MGH research prescription EPIC label as peginterferon lambda-1a or placebo however the display name and administration instructions will be unblinded for provider to be able to choose the correct treatment.

Lambda/Placebo Administration

Each dose of study drug will be dispensed by the MGH CTP in the form of pre-filled syringes. Appropriately delegated, trained and credentialed study staff or contracted study vendor (in the case of home health visits) will administer the stud drug by subcutaneous injection. The injection site should be documented and entered into the EDC. The injection site may be any of the following locations:

- Upper outer arm (right/left)
- Front outer upper thigh (right/left)
- Abdomen
- Upper hip (Right/Left)

For active Lambda treatment only: prior to administration, credentialed staff will expel the air bubble from the syringe and set the dose by aligning the front edge of the stopper with the correct dose indicator line (180 mcg).

Prior and Concomitant Medications

Concomitant medications taken within 30 days prior to screening, up to and including 30 days after the last dose of study drug, need to be recorded in the source documents and electronic case report form(s) (eCRFs).

In drug-drug interaction studies in healthy subjects, the activity of select CYP enzymes were evaluated and suggest that following a single 180µg dose, Lambda is a mild inhibitor of CYP1A2, CYP2C9, and CYP3A4 and a moderate inhibitor of CYP2C19 and CYP2D6. Because the effects of these sensitive CYP substrates are mild or moderate, dose adjustments for other concomitant CYP substrates may not be necessary, but should be used with caution.

Accountability for Lambda/Placebo

The investigator or designee (i.e. pharmacist) is responsible for ensuring adequate accountability of all used and unused study drug. This includes acknowledgement of receipt of each shipment of study drug (quantity and condition). Used study drug will be disposed of in the appropriate sharps container. Administration of Lambda or saline placebo injections will be performed by site staff and accountability of used medication will be documented in the source.

Lambda/placebo accountability records will be utilized to:

- Record the date received and quantity of study product
- Record the date, subject number, subject initials, the study product dispensed
- Record the date, quantity of used and unused study product returned, along with the initials of the person recording the information.

Investigational Product Return or Disposal

Due to the nature of the study product (prefilled syringes for injection), used study medication will not be returned to the study team or research pharmacy and should be disposed of in the appropriate sharps container. The MGH Clinical Trials Pharmacy Established Site Plan will be followed in regard to disposal of unused investigational product.

VI. Study Procedures

The study procedures to be conducted for each subject enrolled in the study are presented in tabular form in [Appendix 2](#) and described in the text that follows.

The investigator must document any deviation from protocol procedures and notify the lead PI and IRB.

Subject Enrollment and Treatment Assignment

Study staff, along with the MGH-established COVID Recruitment team, will review patients in the MGH ED and current admitted patient charts to identify candidate subjects, ideally within the first 24 hours of their admission and/or positive COVID PCR test. Upon identification of a potential subject, the COVID Recruitment team will notify the study team via email regarding a potentially eligible patient. Study staff will prescreen the chart for eligibility and upon confirmation of presumed eligibility, a physician investigator will immediately contact the clinical care team and provide them with information regarding the study. A member of the clinical care team who is already known to the patient will gauge the appropriateness of approaching them. If they deem it appropriate, the clinical care team member will approach the patient to determine if they are willing to learn about this study. If the patient agrees, the clinical care team member will authorize the study staff to approach the patient to discuss the study. The described process is expected to take place within 48 hours of the most recent positive COVID-19 PCR test.

NOTE: per the MGH COVID Recruitment team policy (memo dated 01May2020), any potentially eligible subject identified directly by study staff must be referred back to the team who will then distribute the potential participant accordingly across recruiting COVID trials.

Patients will be consented according to the Partners IRB's Guidelines for Consenting in COVID Research that is More than Minimal Risk. Participants will be enrolled, randomized and dosed from the inpatient floors. In cases with randomized subjects are discharged prior to study completion, home visits with an appropriately credentialed and trained provider (paramedic or registered nurse) will be utilized as available to limit study specific outpatient visits whenever possible. **NOTE: all Day 0 visits (first dose of Lambda/Placebo) must occur onsite at MGH.**

Pretreatment and Baseline Assessments

Baseline Visit

Subjects will be screened no later than within 48 hours of their initial hospital presentation to determine eligibility and provide informed consent for participation in the study.

The following will be performed and documented during screening to assess eligibility

- Obtain informed consent
- Determine inclusion and exclusion eligibility
- Obtain relevant medical history
- Obtain details of concomitant medications
- Complete physical examination including vital signs (resting blood pressure, pulse, respiratory rate and temperature), body weight, and height
- Collect 30ml research blood for storage and future immune biomarker testing
 - Immune biomarkers include IFN- γ , IL-6, IP-10, MCP-1, TNF- α
- Collect sputum and saliva for storage
- Review of clinical lab results for
 - Chemistry
 - Hematology
 - Coagulation
 - Pregnancy testing in WOCBP

Clinical labs drawn within 48 hours prior to consent will be used for screening and as baseline. If clinical labs required to determine protocol eligibility are not available, the clinical care team will be notified and if clinically indicated, testing should be ordered by the care team per standard practice. If testing is not clinically indicated, testing may be completed after informed consent is obtained as part of study screening.

- Request completion of baseline symptom questionnaire
 - Baseline symptom questionnaire must be completed prior to randomization.

From the time of obtaining informed consent through the first administration of study drug (Lambda or saline placebo), all serious adverse events (SAEs), as well as any adverse events related to protocol-mandated procedures, will be recorded in the source and on the adverse events case report form (CRF/eCRF). It is expected the first administration of study drug will occur within 24 hours of informed consent but will occur no later than 72 hours after most recent COVID test, as defined by time of clinical sample collection. All other untoward medical occurrences observed during the screening period, including exacerbation or changes in medical history are to be captured on the medical history CRF/eCRF.

See [Appendix 3](#): Adverse Events and Toxicity Management for additional details.

After review of inclusion and exclusion criteria to confirm continued eligibility, subjects will move into the baseline portion of the visit and be randomized to study drug or placebo assignment. Study drug or placebo will be administered on-site by appropriately credentialed and trailed staff. Up to 30 patients will be consented with a plan of 20 patients randomized to receive Lambda or placebo. A 10 patient cap will be placed on the Lambda treatment group, study enrollment will be halted if this cap is reached.

The following will be performed and documented:

- Review of inclusion/exclusion criteria
- Review of concomitant medications taken since previous visit

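### No safety chemistry or hematology is required between the two doses, and the toxicity stop announces laboratory criteria but lists none

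*Combined protocol and SAP*

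**What the plan says.** Under Toxicity Based Stopping Criteria, Section III states: "Subjects who meet any of the following laboratory or adverse event criteria must stop treatment with study drug". One criterion follows: "Any Grade 4 adverse event assessed as related to study drug". The section then ends, with no sign of redaction. The preceding list of reasons for discontinuation includes unacceptable toxicity, which is defined by reference to this list. It also includes "toxicity that, in the judgment of the investigator, compromises the ability to continue study-specific procedures", or toxicity that makes continuing contrary to the subject's interest. On dosing, the same section says: "There is no option for Lambda dose reduction due to toxicity".

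Doses are given at baseline (Day 0) and Day 7. On safety laboratory work, the visit schedule in Section III says: "On Day 14, subjects will undergo laboratory measurements to confirm CBC and LFT values are within safe parameters". Section VI restricts post-randomization clinical blood tests to Day 14. The schedule of events in Appendix 2 marks chemistry and hematology at Screening/Baseline and Day 14 only. The blood drawn on Day 7 is a research sample for storage.

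On the baseline values, Section VI says: "Clinical labs drawn within 48 hours prior to consent will be used for screening and as baseline". The first dose is expected within 24 hours of consent and "will occur no later than 72 hours after most recent COVID test". Post-randomization visits have a window of one day either side.

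**The concern.** The rule tells sites to expect laboratory stopping criteria and then supplies none. The schedule also produces no safety laboratory result on which such a rule could act before the last dose. Because the dose cannot be reduced, withholding the Day 7 injection is the only dosing response to toxicity after dose 1.

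Toxicity is looked for clinically at Days 3 and 7, through vital signs, symptom-driven examination, the questionnaire and adverse event review. What these can miss is a fall in blood counts or a rise in liver tests that causes no symptoms. The plan gives some reason to watch both. The Introduction names the liver as one of the main sites of the drug's receptor, and Section IV excludes patients on platelets, white cells, neutrophils, hemoglobin and direct bilirubin. The gap is likely to matter most for subjects discharged before Day 7, who may be dosed at home or in clinic with no recent hospital results.

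**Working it through.** The plan gives no figure on this point, so there is none to reproduce. The check sets the stop list against the schedule and then computes intervals.

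**Step 1. Laboratory stopping criteria.** Section III lists 0. The limits in Section IV apply at screening. Section VII sets no stopping threshold. Appendix 3, as published, is a title and a link to a grading scale.

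**Step 2. Schedule (Appendix 2).**

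| | Baseline | Day 3 | Day 5 | Day 7 | Day 14 |
|---|---|---|---|---|---|
| Dose | x | | | x | |
| Chemistry | x | | | | x |
| Hematology | x | | | | x |
| Coagulation | x | | | | |

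Required chemistry or hematology draws after dose 1 and before dose 2: 0. Section VI also lists coagulation on Day 14, which differs from the table, but neither source places it before dose 2.

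**Step 3. Age of the latest required labs at dose 2.** Formula: (labs to consent) + (consent to dose 1) + (dose 1 to dose 2). With the one-day window, dose 2 falls on Days 6 to 8.
- Minimum: 0 + 0 + 6 = 6 days.
- Maximum with expected timing: 2 (labs 48 hours before consent) + 1 (dose within 24 hours of consent) + 8 = 11 days.
- Maximum at the outer limit: 2 + 3 (dose 72 hours after the COVID sample) + 8 = 13 days. This assumes consent at about the time of that sample and not before it.

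**Step 4. First required labs after dosing.** Day 14 with its window is Days 13 to 15.
- After dose 1: 13 to 15 days.
- After dose 2: 13 − 8 = 5 days at the shortest, 15 − 6 = 9 days at the longest.

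**Step 5. Other routes by which a laboratory abnormality could stop dosing.**
- *Investigator judgment (Section III).* Available, but it needs a result to act on.
- *A laboratory abnormality recorded as an adverse event.* Section VII requires this when the abnormality needs intervention, interrupts or stops the drug, or comes with signs or symptoms. Abnormalities without clinical significance are not recorded. Laboratory-related events are graded on clinical severity, which may differ from the laboratory grade. A symptomless Grade 4 value therefore need not become a Grade 4 event, and so need not trigger the only listed stop.
- *Clinical or unscheduled labs (Section VI).* The first depend on availability and the second on the investigator's discretion.

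None of the three requires a test before dose 2.

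**The case against.** **The word laboratory is not empty.** Some laboratory abnormalities become adverse events under Section VII, and the Grade 4 criterion then applies to them. Deleting the word, or adding a cross-reference, would cure the drafting mismatch. That stands for the wording. It leaves dose 2 without a required check.

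**No harm is shown.** Exposure is two injections, the Lambda arm is capped at 10, and entry limits remove patients with poor counts, renal function or direct bilirubin. The Introduction reports tolerability for up to 48 weeks, with over 3000 patients dosed. This stands and limits the weight of the point. That experience is described for chronic hepatitis, however, and the Introduction says human evidence for the COVID-19 use is lacking.

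**Inpatients will often have clinical labs.** This is plausible. The documents give no discharge rate and no frequency of clinical testing, so the number of subjects without recent results cannot be stated.

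**A pre-dose result burdens home visits.** Home visits are meant to "limit study specific outpatient visits whenever possible", and waiting for Day 7 results could force a delay or an extra contact. This is a fair objection to a Day 7 draw for everyone, and the fix below is shaped by it.

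A reader might draw three stronger inferences that the documents do not support:
- *That no laboratory finding can stop dosing.* The routes in Step 5 of the working exist; they are optional.
- *That no laboratory result of any kind is required before dose 2.* The Day 3 PCR swab is required. The gap concerns safety chemistry and hematology.
- *That the Day 14 check shows the protocol contradicting itself.* A blood count and liver check after the last dose is an ordinary end-of-treatment check. It does not show that the authors thought a pre-dose check necessary.

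**Conclusion.** The point holds as a modest safety improvement that should be made. A site that follows the plan exactly can give the last dose with no chemistry or hematology since before the first, and the mandatory stop contains no laboratory criterion.

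The size is 0 laboratory criteria and 0 required safety draws between doses. Required labs are 6 to 11 days old at dose 2 with expected timing, and the next ones come 5 to 9 days after it. The 13-day figure requires every limit to be reached at once, plus the consent-timing assumption, and should not be taken as typical.

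A reader might infer that the second dose is unsafe or that subjects are likely to be harmed. The documents give no rate of blood count or liver toxicity after one dose, so that inference is not supported. The conclusion rests on the schedule and the text of the stop, not on an expected number of events.

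**What to change.** 1. Require one blood count with differential and one chemistry panel (as in Appendix 2) after dose 1, reviewed before the Day 7 injection.
   - Accept clinical results from the preceding 48 hours, in line with the window already used at baseline.
   - For inpatients and clinic visits, draw with the Day 7 research blood, before dosing.
   - For subjects to be dosed at home, draw at the existing Day 3 visit, or use the last inpatient draw after dose 1. No extra contact is then needed.

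2. Add to the list in Section III: *Any new Grade 4 hematology or chemistry value after dose 1, symptomatic or not, unless the investigator documents that it is clearly unrelated to study drug.* The exception keeps abnormalities caused by COVID-19 from stopping dosing automatically.

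3. State that this stop uses CTCAE v4.03 numeric thresholds, that it applies regardless of the clinical-severity grading in Section VII, and that the Appendix 3 scale is not used for it. Otherwise the new stop would conflict with the existing grading rules.

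The cost is a short amendment and at most 20 × 1 = 20 panels, fewer where clinical results qualify. Some discharged subjects have an added blood draw at Day 3. Their labs are also older at dose 2: with Day 3 falling on Days 2 to 4 and dose 2 on Days 6 to 8, they are 6 − 4 = 2 to 8 − 2 = 6 days old, and possibly older if the last inpatient draw is used. An abnormality that first appears after that draw would still be missed, but unlike the present baseline labs, these results postdate dose 1.
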